### 3. STATISTICAL SOFTWARE

All statistical outputs (summary tables, data listings and graphs) will be generated using SAS® version 9.4 or later.

### 4. STATISTICAL TABLES, GRAPHS AND LISTINGS (TABLE OF CONTENTS)

#### 4.1. Statistical Tables

##### Patient Disposition

Table 1: Number of PP patients overall and by site (Type 4)

Table 2: Study flowchart and study exit reasons (Type 6)

Table 3: Study durations (days) (Type 1)

##### Patient Characteristics

###### Baseline

Table 4: Age at surgery (years) (Type 1)

Table 5: Sex (Type 3)

#### CONFIDENTIEL / CONFIDENTIAL

## STATISTICAL ANALYSIS PLAN

Table 6: Weight (kg), Height (cm) and BMI (kg/m^2) (Type 1)  
 Table 7: Medical history / risks factors (Type 6)  
 Table 8: ASA classification (Type 3)  
 Table 9: Patient symptoms related to the disease at hospitalization time (Type 6)  
 Table 10: Patient participation in another W.L. Gore study (Type 3)  
 Table 11: Life-threatening emergency (Type 6)  
 Table 12: Main indication for implantation (Type 6)  
 Table 13: Initial evaluation characteristics for dissection patients (Type 3)  
 Table 14: Initial dissection malperfusion details (Type 6)  
 Table 15: Injury severity of trauma patients (Type 3)  
 Table 16: Glasgow coma scale of trauma patients (Type 1)  
 Table 17: Diameter of the aortic proximal neck (mm) and length of the proximal fixation (mm) (Type 1)  
 Table 18: Characteristic of the proximal neck (Type 3)  
 Table 19: Maximum diameter of the aneurysm/dissection/ulcer (mm) (Type 1)  
 Table 20: Diameter of the distal neck (mm) and length of the distal fixation (mm) (Type 1)  
 Table 21: Characteristic of the distal neck (Type 3)  
 Table 22: Minimal diameter of the main vascular access (mm) (Type 1)  
 Table 23: Significant calcification of the main vascular access (Type 3)  
 Table 24: Mural thrombus and/or calcification in the aortic necks > 50% of the circumference (Type 6)

### *Procedure*

Table 25: Surgeon specialty (Type 3)  
 Table 26: Duration of procedure (min) (Type 1)  
 Table 27: Thoracic endoprosthesis access (Type 5)  
 Table 28: Type of anesthesia used (Type 3)  
 Table 29: Total volume of contrast media used (mL) and total time of exposition to radiation (min) (Type 1)  
 Table 30: Number of devices used per patient (Type 1)  
 Table 31: Successful deployment of endoprosthesis and failure details (Type 6)  
 Table 32: Additional procedure(s) conducted before/during the endovascular surgery (Type 3)  
 Table 33: Imaging abnormalities observed following the procedure (Type 6)  
 Table 34: False lumen perfusion following treatment for dissection (Type 5)  
 Table 35: Persistent endoleak details following the procedure (Type 6)  
 Table 36: Migration details (deployment inaccuracy) identified following the procedure (Type 6)  
 Table 37: Extent of the migration (deployment inaccuracy) identified following the procedure (Type 1)  
 Table 38: Stay in Intensive Care Unit (hours) (Type 1)

### *Follow-up*

Table 39: Maximum diameter of the aneurysm/dissection/lesion (mm) and total length of treatment of the aorta (mm) – by visit (Type 2)  
 Table 40: Dissections characteristics - by visit (Type 4)  
 Table 41: Imaging abnormalities observed - by visit (Type 4)  
 Table 42: Dissection false lumen perfusion characteristics - by visit (Type 7)  
 Table 43: Endoleak details - by visit (Type 7)  
 Table 44: Migration details - by visit (Type 7)

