2.2.2 Secondary endpoint criteria

The secondary endpoints assessing the usefulness of the technique at different follow-up visits (after surgery or in the months following the surgery, at 1 year, 2 years, 3 years, 4 years and 5 years) will be:

- The exclusion rate of aneurysm, of penetrating aortic ulcer, of false lumen or site of rupture, with no endoleak, as defined above
- The rate of neurological complications
- The rate of cardiac, renal and pulmonary complications
- The rate of device-related complications
- The rate of surgical conversion
- The rate of secondary procedures
- The rate of mortality related to the disease

Definitions:

- Migration: movement evaluated on a workstation with 3D reconstruction according to the reference examination (1st post-op imaging examination)
 - Proximal movement > 10 mm or ≤ 10 mm with coverage of a branch of the supra-aortic trunks
 - Distal movement > 10 mm or ≤ 10 mm with coverage of the celiac trunk
- Exclusion of the aneurysm:
 - No type I or type III endoleak associated with the lack of increase in the maximum diameter of the aneurysm sac > 5 mm (reference examination 1st post-operative examination)
- Exclusion of the penetrating ulcer:
 - No type I or type III endoleak associated with the lack of increase in the maximum aortic diameter compared to the ulcer > 5 mm (reference examination 1st post-operative examination)
- Exclusion of rupture site:
 - No type I or type III endoleak
- Exclusion of the false lumen (dissection):
 - Exclusion of the main entry of the dissection
 - Thrombosis of the false lumen at the endoprosthesis
- Mortality from thoracic disease is defined as any death occurring as a result of complication of aortic disease (rupture, conversion, etc.) or following any surgery intended to treat the aortic disease.

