## 2. STATISTICAL METHODS

### 2.1. General Statistical Considerations

#### 2.1.1. Descriptive Statistics in Summary Tables

- Continuous variables will be summarized using standard quantitative statistics: number of non-missing observations, mean, standard deviation, median, quartiles and range (minimum and maximum observed values). The number of missing observations will also be specified.
- Categorical variables will be summarized using classical frequency statistics: number of non-missing observations and percentages by categories. Percentages will be calculated on the number of non-missing observations and will be displayed using one decimal, the corresponding bilateral 95% CI will be presented if appropriate. The number of missing observations will also be specified.

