#### 2.1.3. Handling Missing Data

No replacement of missing data is planned.

If a patient interrupts the study before the end of study, he/she will be considered as missing from his/her last follow-up.

Patients will be considered as censored at the date of the last observation in survival analyses.

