#### 2.4.2.3. Follow-up

The following items will be presented at each visit:

- Measurements and dissections characteristics
- Imaging abnormalities

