#### 5.1.1. With groups (Type 2)

Variable	Group label	N	Missing	Mean	S.D.	Median	Min, Max	Q1-Q3	95% CI*
Variable label	Group 1	XX	XX	XX,X	XX,X	XX,X	XX,X , XX,X	XX,X - XX,X	[XX,X ; XX,X]
	Group 2	XX	XX	XX,X	XX,X	XX,X	XX,X , XX,X	XX,X - XX,X	[XX,X ; XX,X]
	...	...	...	...	...	...	...	...	...
	Group g	XX	XX	XX,X	XX,X	XX,X	XX,X , XX,X	XX,X - XX,X	[XX,X ; XX,X]
	Total*	XX	XX	XX,X	XX,X	XX,X	XX,X , XX,X	XX,X - XX,X	[XX,X ; XX,X]

\*If needed

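### Table 39 compares unpaired mean diameters across visits, pooled over indications, so a drift in either direction can appear when no patient's aorta has changed (minor; no endpoint rests on it)

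*SAP*

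**What the plan says.** SAP 2.4.2.3 lists "Measurements and dissections characteristics" among the items presented at each visit and says nothing of a split by indication. SAP 4.1 turns this into Table 39, "Maximum diameter of the aneurysm/dissection/lesion (mm) and total length of treatment of the aorta (mm"), whose title ends "total length of treatment of the aorta (mm) – by visit (Type 2").

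That layout, shown in SAP section 5.1.1 under "With groups (Type 2"), has one grouping factor, which here is visit. Its columns are N, missing, mean, SD, median, range, quartiles and an optional confidence interval. This matches SAP 2.1.1, where continuous variables get the "number of non-missing observations, mean, standard deviation, median, quartiles and range (minimum and maximum observed values"). Neither place names a change from a reference examination.

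On missing values, SAP 2.1.3 states "No replacement of missing data is planned", and SAP 2.1.1 adds "The number of missing observations will also be specified". Each visit therefore describes the patients measured at that visit. The baseline diameter (Table 19) is also pooled.

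Elsewhere the plan does use within-patient change. Protocol 2.2.2 makes "the lack of increase in the maximum diameter of the aneurysm sac > 5 mm" part of the definition of aneurysm exclusion, with the first post-operative examination as reference. It has a parallel rule for penetrating ulcer. SAP 2.5 carries both into the derived exclusion criteria, which Tables 50 and 52 report by time point. The false-lumen and rupture-site criteria have no diameter component.

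**The concern.** A reader of a 5-year durability report will look along the visits of Table 39 and take a falling mean as regression of the lesion and a rising mean as growth. The table does not support either reading. The four indications can be expected to differ in diameter, and patients leave the later visits through death, withdrawal or missed imaging. If the patients who leave differ in diameter from those who stay, the mean moves although no individual has changed. A real change can also be cancelled.

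The SAP splits mortality and exclusion by main indication but does not split diameter. For aneurysm and ulcer, Tables 50 and 52 capture growth only as one part of a yes/no composite with endoleak, so a reader cannot tell growth from endoleak as the reason for non-exclusion. For dissection and trauma, Table 39 is the only visible tabulated summary of maximum diameter over follow-up.

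**Working it through.** The plan states no figure for diameter change, so there is nothing to reproduce. The check is an illustration. It holds every patient's diameter constant (true change 0) and asks how far the pooled visit mean can move through selection alone.

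**Inputs from the documents:** N = 160 (SAP 1.2); four indications (SAP 2.4.3.1); summary of observed values by visit (Table 39).

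**Assumed inputs, not in the documents:** case mix aneurysm/dissection/ulcer/trauma 45/30/10/15%, that is 72/48/16/24 patients; mean diameters 60/45/42/30 mm; retention as shown below.

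**Formula:** visit mean = Σ(n × r × d) / Σ(n × r), where n is the number enrolled, r the proportion still measured and d the mean diameter in each indication.

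Start: (72×60 + 48×45 + 16×42 + 24×30)/160 = 7872/160 = 49.2 mm.

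Scenario A in full: the numbers measured are 36, 33.6, 9.6 and 21.6, total 100.8. The mean is (2160 + 1512 + 403.2 + 648)/100.8 = 4723.2/100.8 = 46.9 mm, a shift of -2.3 mm.

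| Scenario | Retention % (aneurysm/dissection/ulcer/trauma) | Sum / number measured | Mean (mm) | Shift (mm) |
|---|---|---|---|---|
| A | 50/70/60/90 | 4723.2/100.8 | 46.9 | -2.3 |
| B | 65/65/65/65 | 5116.8/104.0 | 49.2 | 0.0 |
| C | 65/70/65/30 | 4972.8/98.0 | 50.7 | +1.5 |
| D | 65/65/35/20 | 4591.2/88.4 | 51.9 | +2.7 |
| E | 35/70/60/90 | 4075.2/90.0 | 45.3 | -3.9 |

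The paired change is 0 mm in every row, overall and within each indication, because each patient is compared with himself or herself.

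**Masking.** Under A, true growth of 2 mm in every patient would appear as -2.34 + 2 = -0.34 mm, close to no change.

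**A second set of assumptions.** With 70/50/20/20 patients at 62/46/42/27 mm, the start is 8020/160 = 50.1 mm. If 35/33/12/18 are measured at 5 years, the mean is 4678/98 = 47.7 mm, a shift of -2.4 mm with no change in anyone.

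**Splitting by indication is not enough.** Simulated aneurysm diameters (normal, mean 60 mm, SD 10 mm, about 60% retained, logistic dependence of retention on diameter) give these shifts for each odds ratio for retention per 10 mm: -2.0 mm at 0.6, -0.9 mm at 0.8, 0.0 at 1.0 and +0.9 mm at 1.25. Selection on size within one indication also moves an unpaired mean, so the table needs pairing as well as stratification.

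**The case against.** The case against runs as follows. Table 39 is a descriptive follow-up table, and no primary or secondary endpoint uses it. Where the protocol attaches meaning to growth, the SAP already assesses it within patient and by indication, with confidence intervals, in Tables 50 and 52. Table 39 shows N and the missing count, so attrition is visible, and Listing 18 gives measurements by visit. Every input to the illustration is assumed. All of this stands, and it is why the point is minor.

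It does not remove the point. A missing count tells the reader that patients left, not how their diameters differed from those who stayed. A listing does not correct the mean that will be read. Tables 50 and 52 do not separate growth from endoleak and do not cover dissection or trauma.

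Three stronger readings are tempting, and the documents do not support them.

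- **A reader might infer that the table will show false shrinkage.** Nothing fixes the direction. Protocol 5.1 accepts different intervals or less invasive tests where the previous examination was clean. If those patients have smaller lesions, the mean could rise.
- **A reader might set the drift against the 5 mm limit.** That limit is a within-patient criterion, and it applies only to aneurysm and ulcer exclusion. A shift in a cohort mean reclassifies no patient.
- **A reader might infer that explanted patients drop out of the table.** Protocol 5.4.1 asks for their clinical evaluation to continue to the 5-year visit. Whether their diameter is then recorded is not stated.

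Parts of both documents are not visible, and the categories inside Table 41 (imaging abnormalities) are not listed. A separate count of growth somewhere in the plan therefore cannot be ruled out.

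**Conclusion.** The point holds as a minor weakness of a descriptive table. As specified, Table 39 is an unpaired, available-case summary pooled over indications, and differences between its visits cannot be read as change in the aorta. With no true change, the assumed scenarios give shifts from -3.9 to +2.7 mm, and none when loss is unrelated to diameter or indication. These figures show what is possible under the stated assumptions and do not predict this cohort. The primary endpoint and the exclusion endpoints are unaffected.

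**What to change.** In Table 39, report the paired within-patient change from the first post-operative examination, by main indication and visit. Give the number of pairs, the reference diameter of those same patients, and the mean, SD, median and 95% CI of the change. For aneurysm and ulcer, add the number and percentage with growth above 5 mm, which is the protocol's own threshold. Keep the absolute diameters, split by indication.

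The cost is some programming. The paired difference is already needed to derive aneurysm and ulcer exclusion, and diameter is already tabulated by visit, so no new data are required.

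There are three limits:

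- Patients with a single post-operative examination contribute no pair.
- Some cells will be small. Under the assumed mix there are 16 ulcer patients, and 60% retention leaves about 10 pairs (16 × 0.60 = 9.6).
- Pairing removes drift caused by differences in size between patients. It does not correct for loss that depends on growth itself, so the number of pairs should be read alongside each estimate.

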### CONFIDENTIEL / CONFIDENTIAL

# STATISTICAL ANALYSIS PLAN

Gore-TAG\_SAP\_V2.2

TAG Registry

Page 13/18

Table 45: Extent of the migration - by visit (Type 2)

## Endpoints Analyses

### Primary Analysis

Table 46: Mortality – by time point (Type 4)

Table 47: Mortality by life-threatening emergency – by time point (Type 4)

Table 48: Mortality by main indication for implantation – by time point (Type 4)

### Secondary Analyses

Table 49: Rate of exclusion of aneurysm, false lumen, penetrating aortic ulcer or rupture site, with no type I or III endoleak - by time point (Type 4)

Table 50: Rate of exclusion of aneurysm with no type I or III endoleak - by time point (Type 4)

Table 51: Rate of exclusion of false lumen with no type I or III endoleak - by time point (Type 4)

Table 52: Rate of exclusion of penetrating aortic ulcer with no type I or III endoleak - by time point (Type 4)

Table 53: Rate of exclusion of rupture site, with no type I or III endoleak - by time point (Type 4)

Table 54: Neurological complications rate - by time point (Type 4)

Table 55: Cardiac, renal and pulmonary complications rate - by time point (Type 4)

Table 56: Device-related complications rate - by time point (Type 4)

Table 57: Surgical conversion rate - by time point (Type 4)

Table 58: Secondary procedures rate - by time point (Type 4)

Table 59: Mortality rate related to the disease - by time point (Type 4)

## Safety

### Secondary procedures

Table 60: Secondary procedures rate (Type 3)

Table 61: Reasons of secondary procedures (Type 6)

Table 62: Endovascular/Surgical treatment (secondary procedures) (Type 5)

Table 63: Imaging abnormalities observed following secondary procedures (Type 3)

Table 64: False lumen perfusion following secondary procedures - by visit (Type 7)

Table 65: Endoleak details following secondary procedures - by visit (Type 7)

### Adverse events

Table 66: Adverse events (Type 8)

Table 67: Reasons of SAE seriousness (Type 6)

## 4.2. Graphs

Graph 1: Mortality survival analysis (Type 9)

Graph 2: Mortality by life-threatening emergency - survival analysis (Type 9)

Graph 3: Mortality by main indication for implantation survival analysis (Type 9)

Graph 4: Neurological complications survival analysis (Type 9)

Graph 5: Cardiac, renal and pulmonary complications survival analysis (Type 9)

Graph 6: Device-related complications survival analysis (Type 9)

Graph 7: Surgical conversion survival analysis (Type 9)

Graph 8: Secondary procedures survival analysis (Type 9)

Graph 9: Mortality related to the disease survival analysis (Type 9)

#### **4.3. Listings**

##### **Patient Disposition**

Listing 1: Reasons of non-inclusion in the study or exclusion from PP population  
 Listing 2: Patient follow-up, study durations and reasons of study exit and

##### **Patient Characteristics**

###### *Baseline*

Listing 3: Demographics  
 Listing 4: Medical history / risks factors  
 Listing 5: Patient symptoms related to the disease at hospitalization time  
 Listing 6: Patient participation in another W.L. Gore study  
 Listing 7: Life-threatening emergency and main indication for implantation  
 Listing 8: Initial evaluation characteristics for dissection patients  
 Listing 9: Injury severity of trauma patients  
 Listing 10: Procedure planning

###### *Procedure*

Listing 11: Implantation parameters  
 Listing 12: Devices used details  
 Listing 13: Successful deployment of endoprosthesis, failure details and additional procedure(s) conducted before/during the endovascular surgery  
 Listing 14: Imaging abnormalities observed following the procedure  
 Listing 15: False lumen perfusion following treatment for dissection  
 Listing 16: Persistent endoleak details following the procedure  
 Listing 17: Migrations details (deployment inaccuracy) identified following the procedure

###### *Follow-up*

Listing 18: Measurements and dissection characteristics – by visit  
 Listing 19: Imaging abnormalities observed – by visit  
 Listing 20: Dissection false lumen perfusion characteristics – by visit  
 Listing 21: Endoleak details – by visit  
 Listing 22: Migrations details – by visit

##### **Endpoints Analyses**

Listing 23: Primary and secondary endpoints

##### **Safety**

Listing 24: Secondary procedures  
 Listing 25: Adverse events

	STATISTICAL ANALYSIS PLAN	Gore-TAG_SAP_V2.2 TAG Registry Page 15/18
--	----------------------------------	---

## 5. LAYOUT OF THE STATISTICAL TABLES

### 5.1. Continuous variables

#### 5.1.1. No group (Type 1)

Variable	N	Missing	Mean	S.D.	Median	Min, Max	Q1-Q3	95% CI*
Variable label	XX	XX	XX,X	XX,X	XX,X	XX,X , XX,X	XX,X - XX,X	[XX,X ; XX,X]

\*If needed

#### 5.1.1. With groups (Type 2)

Variable	Group label	N	Missing	Mean	S.D.	Median	Min, Max	Q1-Q3	95% CI*
Variable label	Group 1	XX	XX	XX,X	XX,X	XX,X	XX,X , XX,X	XX,X - XX,X	[XX,X ; XX,X]
	Group 2	XX	XX	XX,X	XX,X	XX,X	XX,X , XX,X	XX,X - XX,X	[XX,X ; XX,X]
	...	...	...	...	...	...	...	...	...
	Group g	XX	XX	XX,X	XX,X	XX,X	XX,X , XX,X	XX,X - XX,X	[XX,X ; XX,X]
	Total*	XX	XX	XX,X	XX,X	XX,X	XX,X , XX,X	XX,X - XX,X	[XX,X ; XX,X]

\*If needed

### 5.2. Categorical variables

#### 5.2.1. No group (Type 3)

		Population (N=XX)
Variable label	N	XX
	Variable 1	XX (XX.X%)
	95% CI (Variable 1)*	[XX.X% - XX.X%]
	Variable 2	XX (XX.X%)
	95% CI (Variable 2)*	[XX.X% - XX.X%]
	...	...
	Variable n	XX (XX.X%)
	95% CI (Variable n)*	[XX.X% - XX.X%]
	Missing	XX

\*If needed

#### 5.2.2. With groups (Type 4)

		Group label				
		Group 1 (N=XX)	Group 2 (N=XX)	....	Group n (N=XX)	Total* (N=XX)
Variable label	N	XX	XX	...	XX	XX
	Variable 1	XX (XX.X%)	XX (XX.X%)	...	XX (XX.X%)	XX (XX.X%)
	95% CI (Variable 1)*	[XX.X% - XX.X%]	[XX.X% - XX.X%]	...	[XX.X% - XX.X%]	[XX.X% - XX.X%]
	Variable 2	XX (XX.X%)	XX (XX.X%)	...	XX (XX.X%)	XX (XX.X%)
	95% CI (Variable 2)*	[XX.X% - XX.X%]	[XX.X% - XX.X%]	...	[XX.X% - XX.X%]	[XX.X% - XX.X%]
	...	...	...	...	...	...
	Variable n	XX (XX.X%)	XX (XX.X%)	...	XX (XX.X%)	XX (XX.X%)
	95% CI (Variable n)*	[XX.X% - XX.X%]	[XX.X% - XX.X%]	...	[XX.X% - XX.X%]	[XX.X% - XX.X%]

**CONFIDENTIEL / CONFIDENTIAL**

Toute reproduction ou distribution, totale ou partielle, de ce document, sans autorisation préalable de MedPass International est interdite.  
Reproduction and distribution of this document, in whole or in part, is strictly forbidden without prior authorization from MedPass International.

	STATISTICAL ANALYSIS PLAN	Gore-TAG_SAP_V2.2 TAG Registry Page 16/18
--	----------------------------------	---

		Group label				
		Group 1 (N=XX)	Group 2 (N=XX)	....	Group n (N=XX)	Total* (N=XX)
	Missing	XX	XX	...	XX	XX

\*If needed

### 5.3. Others

#### 5.3.1. Several variables or variables with more than one modality by patient (Type 5)

Variable 1 / Variable 2	Population (N=XX)	95% CI
Variable 1 modality 1	XX (XX.X%)	[XX.X% - XX.X%]
Variable 1 modality 2	XX (XX.X%)	[XX.X% - XX.X%]
...	...	...
Variable 1 modality n	XX (XX.X%)	[XX.X% - XX.X%]

(sum of all modality ≥ total number of patient)

\*If needed

#### 5.3.2. Conditional variables (Type 6)

Variable 1 / Variable 2	Population (N=XX)	95% CI*
Variable 1 modality 1	XX (XX.X%)	XX (XX.X%)
Variable 2 modality 1	XX (XX.X%)	XX (XX.X%)
Variable 2 modality 2	XX (XX.X%)	XX (XX.X%)
...	...	...
Variable 2 modality n	XX (XX.X%)	XX (XX.X%)
Variable 1 modality 2	XX (XX.X%)	XX (XX.X%)
Variable 2 modality 1	XX (XX.X%)	XX (XX.X%)
Variable 2 modality 2	XX (XX.X%)	XX (XX.X%)
...	...	...
Variable 2 modality n	XX (XX.X%)	XX (XX.X%)
...	...	...
Variable 1 modality n	XX (XX.X%)	XX (XX.X%)
Variable 2 modality 1	XX (XX.X%)	XX (XX.X%)
Variable 2 modality 2	XX (XX.X%)	XX (XX.X%)
...	...	...
Variable 2 modality n	XX (XX.X%)	XX (XX.X%)

\*If needed

#### 5.3.1. Conditional variables with groups (Type 7)

Variable 1 / Variable 2	Group 1 (N=XX)	95% CI* (Group 1)	Group 2 (N=XX)	95% CI* (Group 2)	...	Group n (N=XX)	95% CI* (Group n)
Variable 1 modality 1	XX (XX.X%)	XX (XX.X%)	XX (XX.X%)	XX (XX.X%)	...	XX (XX.X%)	XX (XX.X%)
Variable 2 modality 1	XX (XX.X%)	XX (XX.X%)	XX (XX.X%)	XX (XX.X%)	...	XX (XX.X%)	XX (XX.X%)
Variable 2 modality 2	XX (XX.X%)	XX (XX.X%)	XX (XX.X%)	XX (XX.X%)	...	XX (XX.X%)	XX (XX.X%)
...	...	...	...	...	...	...	...

#### CONFIDENTIEL / CONFIDENTIAL

Toute reproduction ou distribution, totale ou partielle, de ce document, sans autorisation préalable de MedPass International est interdite.  
Reproduction and distribution of this document, in whole or in part, is strictly forbidden without prior authorization from MedPass International.

	STATISTICAL ANALYSIS PLAN	Gore-TAG_SAP_V2.2 TAG Registry Page 17/18
--	----------------------------------	---

Variable 1 / Variable 2	Group 1 (N=XX)	95% CI* (Group 1)	Group 2 (N=XX)	95% CI* (Group 2)	...	Group n (N=XX)	95% CI* (Group n)
Variable 2 modality n	XX (XX.X%)	XX (XX.X%)	XX (XX.X%)	XX (XX.X%)	...	XX (XX.X%)	XX (XX.X%)
Variable 1 modality 2	XX (XX.X%)	XX (XX.X%)	XX (XX.X%)	XX (XX.X%)	...	XX (XX.X%)	XX (XX.X%)
Variable 2 modality 1	XX (XX.X%)	XX (XX.X%)	XX (XX.X%)	XX (XX.X%)	...	XX (XX.X%)	XX (XX.X%)
Variable 2 modality 2	XX (XX.X%)	XX (XX.X%)	XX (XX.X%)	XX (XX.X%)	...	XX (XX.X%)	XX (XX.X%)
...	...	...	...	...	...	...	...
Variable 2 modality n	XX (XX.X%)	XX (XX.X%)	XX (XX.X%)	XX (XX.X%)	...	XX (XX.X%)	XX (XX.X%)
...	...	...	...	...	...	...	...
Variable 1 modality n	XX (XX.X%)	XX (XX.X%)	XX (XX.X%)	XX (XX.X%)	...	XX (XX.X%)	XX (XX.X%)
Variable 2 modality 1	XX (XX.X%)	XX (XX.X%)	XX (XX.X%)	XX (XX.X%)	...	XX (XX.X%)	XX (XX.X%)
Variable 2 modality 2	XX (XX.X%)	XX (XX.X%)	XX (XX.X%)	XX (XX.X%)	...	XX (XX.X%)	XX (XX.X%)
...	...	...	...	...	...	...	...
Variable 2 modality n	XX (XX.X%)	XX (XX.X%)	XX (XX.X%)	XX (XX.X%)	...	XX (XX.X%)	XX (XX.X%)

\*If needed

